### **6.2.3. Visit 4 (Week 8: Day 57 ±3 days)**

Procedures that will be performed on Visit 4 include:

- Drug accountability (include review of dosing diary) and dispense of new investigational product and dispense dosing diary
- Concomitant treatments/medication review
- Safety assessment and AE reporting
- Schedule the subject to return for Visit 5 (Week 12)

### **6.2.4. Visit 5 (Week 12: Day 85 ±3 days) End of Study or Early Termination**

Subjects are required to fast for at least 9 hours prior to the visit. Procedures that will be performed on Visit 5 include:

- Targeted physical examination: weight, examination of heart, lungs, lower extremities for peripheral edema, abdomen and lymph nodes. Assessment of new physical findings.
- Vital signs/temperature.
- Laboratory tests: Hematology, chemistry panel (including fasting lipid profile), urine pregnancy tests ( $\beta$ -HCG, female subjects who have child-bearing potential only), urinalysis, lymphocyte subset markers, CRP and ESR (refer to Section [7.2.6](#)).
- Joint assessment: tender/painful joint count (68 joints) and swollen joint count (66 joints).
- Completion of the following assessments:
  - Patient assessment of arthritis pain
  - Patient global assessment of arthritis
  - Physician global assessment of arthritis
- Patient reported outcome (PRO):
  - HAQ-DI
  - SF-36 (ver.2, acute)
  - FACIT-Fatigue
  - EQ-5D
- Drug accountability (include review of dosing diary)

- Concomitant treatments/medications review
- Safety assessment and AE reporting

### **6.3. Follow-up Visit**

A follow-up visit is not planned in this study. However, when a follow-up visit is necessary due to an adverse event or abnormal test finding, the investigator may arrange follow-up at investigator's discretion for subjects.

### **6.4. Subject Withdrawal**

Subjects may withdraw from the study at any time at their own request, or they may be withdrawn at any time at the discretion of the investigator or sponsor for safety or behavioral reasons, or the inability of the subject to comply with the protocol required schedule of study visits or procedures at a given study site.

If subjects withdraw prior to Week 12 (Visit 5), the subject should complete the procedures for Week 12 (Visit 5) (refer to section 6.2.4).

It is important to continue all subjects in the study and perform all tests and procedures until the study is completed to enable collection of safety data, even if a subject withdraws from the study assigned treatment, unless the subject withdraws their consent to continue participation.

If a subject does not return for a scheduled visit, every effort should be made to contact the subject and document their current status. All attempts to contact the subject and information received during contact attempts must be documented in the subject's medical record. In any circumstance, every effort should be made to document subject outcome, if possible. The investigator should inquire about the reason for withdrawal, request the subject to return all unused investigational products, request the subject to return for a final visit, if applicable, and follow up with the subject regarding any unresolved Adverse Events (AEs).

If the subject withdraws from the study, and also withdraws consent for disclosure of future information, no further evaluations should be performed, and no additional data should be collected. The sponsor may retain and continue to use any data collected before such withdrawal of consent.

## **7. ASSESSMENTS**

Every effort should be made to ensure that the protocol-required tests and procedures are completed as described. However, it is anticipated that from time to time there may be circumstances, outside of the control of the investigator, that may make it unfeasible to perform the test. In these cases the investigator will take all steps necessary to ensure the safety and well-being of the subject. When a protocol-required test cannot be performed, the investigator will document the reason for this and any corrective and preventive actions that he or she has taken to ensure that normal processes are adhered to as soon as possible. The study team will be informed of these incidents in a timely fashion.

## 7.1. Efficacy

### 7.1.1. Assessments of Disease Activity

Individual components for the following indicators of disease activity will be collected throughout the study as described in Table 4.

**Table 4. Disease Activity Indicators**

Indicator	Definition/Calculation
DAS28-4(CRP)	$0.56*\sqrt{(TJC28)} + 0.28*\sqrt{(SJC28)} + 0.36*\ln(\text{CRP in mg/L} + 1) + 0.014*\text{PtGA in mm} + 0.96$
DAS28-4(ESR)	$0.56*\sqrt{(TJC28)} + 0.28*\sqrt{(SJC28)} + 0.70*\ln(\text{ESR in mm/hour}) + 0.014*\text{PtGA in mm}$
ACR Response Rates	The ACR's definition for calculating a 20% improvement in RA (ACR20) is as follows: a 20% improvement in tender and swollen joint counts and 20% improvement in 3 of the 5 remaining ACR-core set measures: patient and physician global assessments, pain, disability, and an acute-phase reactant (e.g., CRP). Similarly, ACR50 and 70 are calculated with the respective percent improvements.

DAS = Disease Activity Score; CRP = C-reactive protein in mg/L; TJC = tender joint count; SJC = swollen joint count; ESR = erythrocyte sedimentation rate in mm/first hour, PtGA = patient's global assessment of health; ACR = American College of Rheumatology

### 7.1.2. DAS Assessments

The Disease Activity Score (DAS) assessment is a derived measurement with differential weighting given to each component. The DAS 28-4(CRP) and the DAS28-4(ESR) will be calculated.

The components of the DAS 28 arthritis assessment are:

1. Tender/Painful Joint Count (28 joints);
2. Swollen Joint Count (28 joints);
3. CRP or ESR;
4. Patient Global Assessment of Arthritis.

#### 7.1.2.1. Tender/Painful Joint Count (28 joints)

Twenty-eight (28) joints will be assessed by investigator to determine the number of joints that are considered tender or painful. The response to pressure/motion on each joint will be assessed using the following scale:

- Present/Absent/Not Done/Not Applicable (to be used for artificial joints).

The 28 joints to be assessed are the shoulders, elbows, wrists, metacarpophalangeal (MCP) joints, proximal interphalangeal (PIP) joints, and knees. Artificial joints will not be assessed. As a general rule, the same investigator should perform these assessments throughout the term of study.

#### 7.1.2.2. Swollen Joint Count (28 joints)

The investigator will also assess these joints for swelling using the following scale:

- Present/Absent/Not Done/Not Applicable (to be used for artificial joints).

The 28 swollen joint count includes the following joints: shoulders, elbows, wrists, MCP joints, PIP joints and knees. Artificial joints will not be assessed. As a general rule, the same investigator should perform these assessments throughout the term of study.

#### **7.1.2.3. C-Reactive Protein (CRP)**

The CRP will be analyzed by a central laboratory. It will be used in the calculation of several efficacy parameters. CRP results will not be blinded and will be provided to the investigator for all visits.

#### **7.1.2.4. Erythrocyte Sedimentation Rate (ESR) (At Participating Sites)**

The ESR will be analyzed by a local laboratory using the Westergren method or other methods that yield results comparable to the Westergren method (the same ESR assessment method should be used consistently for a subject throughout the study). ESR results will be used in the calculation of several efficacy parameters. ESR results will not be blinded.

#### **7.1.3. ACR Assessments**

The American College of Rheumatology's definition for calculating improvement in RA (ACR20) is calculated as a 20% improvement in tender and swollen joint counts and 20% improvement in 3 of the 5 remaining ACR-core set measures: patient and physician global assessments, pain, disability, and an acute-phase reactant. Similarly, ACR50 and 70 are calculated with the respective percent improvements.

The specific components of the ACR Assessments that will be used in this study are:

1. Tender/Painful Joint count (68 joints);
2. Swollen Joint Count (66 joints);
3. Patient Assessment of Arthritis Pain;
4. Patient Global Assessment of Arthritis;
5. Physician Global Assessment of Arthritis;
6. CRP;
7. HAQ-DI.

#### **7.1.3.1. Tender/Painful Joint Count (68 joints)**

Sixty-eight (68) joints will be assessed by investigator to determine the number of joints that are considered tender/painful. The response to pressure/motion on each joint will be assessed using the following scale:

- Present/Absent/Not Done/Not Applicable (to be used for artificial joints).

As a general rule, the same investigator performed these assessments throughout the term of study.

The 68 joints to be assessed are the following (Artificial joints will not be assessed):

- Upper Body: temporomandibular, sternoclavicular, acromioclavicular;
- Upper Extremity: shoulder, elbow, wrist (includes radiocarpal, carpal and carpometacarpal considered as one unit), metacarpophalangeals (MCP I, II, III, IV, V), thumb interphalangeal (IP), proximal interphalangeals (PIP II, III, IV, V), distal interphalangeals (DIP II, III, IV, V);
- Lower Extremity: hip, knee, ankle, tarsus (includes subtalar, transverse tarsal and tarsometatarsal considered as one unit), metatarsophalangeals (MTP I, II, III, IV, V), great toe interphalangeal (IP), proximal and distal interphalangeals combined (PIP II, III, IV, V).

#### **7.1.3.2. Swollen Joint Count (66 joints)**

Investigator will also assess these joints for swelling using the following scale:

- Present/ Absent/Not Done/Not Applicable (to be used for artificial joints).

Sixty-six (66) joints will be assessed for swelling, the same as those listed above for tenderness/pain, except that the right and left hip joints are not included in the swollen joint count. Artificial joints will not be assessed. As a general rule, the same investigator should perform these assessments throughout the term of study.

#### **7.1.3.3. Patient Assessment of Arthritis Pain**

Subjects will assess the severity of their arthritis pain using a 100 mm visual analog scale (VAS) placing a mark on the scale between 0 (no pain) and 100 (most severe pain), which corresponds to the magnitude of their pain.

#### **7.1.3.4. Patient Global Assessment of Arthritis**

Subjects will answer the following question, “Considering all the ways your arthritis affects you, how are you feeling today?” The subject’s response will be recorded using a 100 mm VAS.

#### **7.1.3.5. Physician Global Assessment of Arthritis**

The investigator will assess how the subject’s overall arthritis appears at the time of the visit. This is an evaluation based on the subject’s disease signs, functional capacity and physical examination, and should be independent of the Patient Global Assessment of Arthritis. The investigator’s response will be recorded using a 100 mm VAS.

### **7.1.4. Patient Reported Outcomes**

#### **7.1.4.1. Health Assessment Questionnaire-Disability Index (HAQ-DI)**

The HAQ-DI assesses the degree of difficulty a subject has experienced during the past week in 8 domains of daily living activities: dressing and grooming, arising, eating,

walking, hygiene, reach, grip, and other activities. Each activity category consists of 2-3 items. For each question in the questionnaire, the level of difficulty is scored from 0 to 3 with 0 representing “no difficulty,” 1 as “some difficulty,” 2 as “much difficulty,” and 3 as “unable to do”. Any activity that requires assistance from another individual or requires the use of an assistive device adjusts to a minimum score of 2 to represent a more limited functional status. The form should then be checked by the site staff for completeness (refer to [Appendix 6](#)).

#### **7.1.4.2. SF-36 Health Survey (Version 2, Acute)**

The SF-36 is a widely used general health status questionnaire that assesses 8 domains of functional health and well-being: Physical Functioning, Role Limitations due to Physical Health Problems, Bodily Pain, Social Functioning, Mental Health, Role Limitations due to Emotional Problems, Vitality, and General Health Perceptions. A Physical health component summary score and Mental health component summary score are calculated from the 8 domain scores. The acute form uses a recall period of one week. The SF-36 is a psychometrically valid and reliable instrument that has been translated into many languages, and the scores have been shown to be responsive to change. Higher scores indicate a better health-related quality of life. On the specified study visit days, subjects should complete the SF-36. The SF-36 should be checked for completeness by the study site staff (refer to [Appendix 7](#)).

#### **7.1.4.3. Functional assessment of chronic illness therapy (FACIT)-Fatigue**

The FACIT-Fatigue Scale is a subject completed questionnaire consisting of 13 items that assess fatigue. Instrument scoring yields a range from 0 to 52, with higher scores representing better subject status (less fatigue). This questionnaire should be completed by the subject prior to any procedures being performed at the visit, if possible. The form should then be checked by site staff for completeness (refer to [Appendix 8](#)).

#### **7.1.4.4. Euro Quality of Life Questionnaire (EQ-5D)**

The EQ-5D is a patient completed instrument designed to assess impact on quality of life in five domains: mobility, self-care, usual activities, pain/discomfort, and anxiety/depression. Additionally, scores from the five domains may be used to calculate a single index value. The instrument provides a simple descriptive profile and a single index value for health status, and is applicable to a wide range of health conditions and treatments. On the specified study visit days, subjects should complete the EQ-5D at the clinic. The EQ-5D should be checked for completeness by the study site staff (refer to [Appendix 9](#)).

### **7.2. Safety**

#### **7.2.1. Complete Physical Examination**

A standard physical examination will be performed at the screening visit. The following parameters and body systems will be examined and any abnormalities described: height, weight, general appearance, skin (presence of rash), HEENT (head, eyes, ears, nose and throat), lungs (auscultation), heart (auscultation for presence of murmurs, gallops, rubs), lower extremities (peripheral edema), abdominal (palpation and auscultation), neurologic (mental status, station, gait, reflexes, motor and sensory function, coordination) and lymph nodes.

### **7.2.2. Targeted Physical Examinations**

At Visit 2, 3 and 5, a targeted physical examination will be performed assessing the following: weight, lungs, heart, lower extremities for peripheral edema, abdomen and lymph nodes. Any clinically significant changes from the last complete physical examination should be recorded as AEs; ongoing AEs should be updated, as appropriate.

### **7.2.3. Vital signs and body temperature**

Blood pressure should be measured in the subject's dominant arm and recorded to the nearest mmHg. The same arm will be used throughout the study. All blood pressure in this study will be measured with the subject in the sitting position after resting for at least 5 minutes. The use of automated devices for measuring blood pressure and pulse rate are acceptable, although, when done manually, pulse rate will be measured in the brachial/radial artery for at least 30 seconds. When the timing of these measurements coincides with a blood collection, blood pressure and pulse rate should be obtained first. Temperature will be collected as axillary temperature.

### **7.2.4. 12-lead electrocardiogram**

A 12-lead ECG will be obtained on all subjects at the screening visit. All ECGs should be performed after the subject has rested quietly for at least 10 minutes. ECGs will be read locally. Screening ECG results will be used as a screening tool and should be maintained in the subject's source documentation. Subjects with a screening 12-lead electrocardiogram that demonstrates clinically significant abnormalities requiring urgent treatment (e.g., acute myocardial infarction, serious tachy- or bradyarrhythmias) or that is indicative of serious underlying heart disease (e.g., cardiomyopathy, major congenital heart disease, low voltage in all leads) should not be enrolled in the study.

### **7.2.5. Chest Radiograph or chest CT scan**

Subject must have a chest radiograph (PA and lateral views) or chest CT scan with no evidence of current, active TB or previous inactive TB, general infections, heart failure or malignancy taken at screening or within 12 weeks prior to screening and read by a qualified radiologist or respiratologist. Documentation of the official reading must be located and available in the source documentation.

If necessary, a chest CT scan (with or without IV contrast) may be performed during screening following initial performance of chest radiographs (PA and lateral) at the clinical discretion of the investigator. If pulmonary signs and symptoms are observed at and after baseline visit, unscheduled imaging tests (e.g. chest X-ray or chest CT scan) may be performed based on the judgment by investigator as appropriate.

### **7.2.6. Clinical Laboratory Tests**

Blood and urine samples will be collected at the time points identified in [Table 5](#). Unscheduled clinical laboratory tests may be obtained at any time during the study to assess any perceived safety concerns.

**Table 5. Clinical Laboratory Tests**

Tests	Visits	Comments
Chemistry blood urea nitrogen, creatinine, glucose, calcium, sodium, potassium, bicarbonate, chloride, total protein, total bilirubin, direct bilirubin, indirect bilirubin, ALT, AST, ALP, gamma-glutamyl transferase (GGT), albumin, creatine kinase (CK)	Visit 1, Visit 2, Visit 3 and Visit 5	Creatinine clearance is calculated by the central laboratory according to the Cockcroft-Gault Formula at screening Visit ( Appendix 4 ).  Refer to Section 7.5 for retesting requirements for ALT and AST elevated $\geq 3 \times$ ULN.
Hematology Hemoglobin Hematocrit RBC WBC Neutrophils (% , abs) Lymphocytes (% , abs) Monocytes (% , abs) Eosinophils (% , abs) Basophils (% , abs) Platelets	Visit 1, Visit 2, Visit 3 and Visit 5	Refer to Section 7.5 for monitoring requirements related to hemoglobin, neutrophil and lymphocyte counts.
C-reactive Protein (CRP)	Visit 1, Visit 2, Visit 3 and Visit 5	Refer to Section 7.1.2.3.
Erythrocyte sedimentation ratio (ESR)	Visit 1, Visit 2, Visit 3 and Visit 5	Refer to Section 7.1.2.4.
Rheumatoid Factor	Visit 1	
Banked Biospecimens	Visit 2	Refer to Section 7.3.
Serum $\beta$ -D-glucan and KL-6	Visit 1	
HIV Serology	Visit 1	
Hepatitis B Surface antigen (HBsAg)	Visit 1	Refer to Section 7.2.6.2 and Appendix 5 .
Hepatitis B Core Antibody (HBcAb)		
Hepatitis B Surface Antibody (HBsAb)		
Hepatitis B virus DNA (HBV DNA)	Visit 1, recommended every 4 weeks	Refer to Section 7.2.6.2 and Appendix 5 to determine when necessary.
Hepatitis C virus antibody (HCV Ab)	Visit 1	HCV RNA assay will be performed, if HCV Ab is positive.
Hepatitis C RNA (HCV RNA)		Subjects should be fasting for at least 9 hours prior to each visit. Refer to Section 7.2.6.4.
Lipids (fasting) Triglycerides Total Cholesterol HDL Cholesterol LDL Cholesterol	Visit 1, Visit 2, Visit 3 and Visit 5	
Serum Pregnancy Testing	Visit 1	All female subjects of childbearing potential, regardless of whether or not they are sexually active. Refer to Section 7.2.6.1 .
Whole blood IFN- $\gamma$ release assay (Quantiferon-3G/QuantiFERON® -TB Gold In-Tube or T-SPOT)	Visit 1	If there are two consecutive indeterminate results of QFT- G/QuantiFERON® -TB Gold In-Tube or T-SPOT test, a Mantoux Purified Protein Derivative (PPD) tuberculin skin test can be performed during screening period. Refer to Section 7.2.6.3.1.

**Table 5. Clinical Laboratory Tests**

Tests	Visits	Comments
Varicella-Zoster Virus (VZV) Lymphocyte subset markers	Visit 1 Visit 2, Visit 3 and Visit 5	Lymphocyte subset markers include: CD3+, CD3-CD19+, CD3+CD4+CD8-, CD3+CD4-CD8+, CD3+CD16+CD56+, CD3-CD16+CD56+, CD3-CD16-CD56+, CD3-CD16-CD56+, CD4/CD8
Urinalysis Specific Gravity pH Protein Glucose Ketones Blood Nitrite Leukocyte Esterase Pregnancy test (excluding visit 1) Urine sediment (microscopy) Urine culture (if clinically indicated)	Visit 1, Visit 2, Visit 3 and Visit 5	
Tests to include when repeat AST and/or ALT are required: Albumin Creatine kinase (CK) Total bilirubin Direct bilirubin Indirect bilirubin, GGT PT/INR ALP	At same time as AST and/or ALT are repeated for elevations as noted in Section 7.5	Refer to Section 8.7.2 for further details on management of elevations.

---

ALT = alanine aminotransferase (SGPT); AST = aspartate aminotransferase (SGOT) ; ALP = alkaline phosphatase; HDL = high density lipoprotein; HIV = human immunodeficiency virus; LDL = low density lipoprotein; SGOT = serum glutamic-oxaloacetic transaminase (AST); SGPT = serum glutamic pyruvate transaminase (ALT); TB = tuberculosis;  
× ULN = times the upper limit of normal;

### 7.2.6.1. Pregnancy Testing

For female subjects of childbearing potential, a serum pregnancy test will be performed at the screening visit. For female subjects of childbearing potential, urine pregnancy test with sensitivity of at least 25 mIU/mL will be performed prior to starting study therapy (before investigational product administration at the baseline visit), visit 3 (week 4) and visit 5 (week 12). A negative pregnancy result is required before the subject may receive the investigational product. Urine pregnancy test may be repeated more frequently if a menstrual cycle is missed or if potential pregnancy is otherwise suspected.

### 7.2.6.2. Hepatitis B virus screening

All subjects must undergo testing for hepatitis B surface antigen (HBsAg), hepatitis B core antibody (HBcAb) and hepatitis B surface antibody (HBsAb). Subjects who have

negative HBsAg, negative HBcAb and positive HBsAb without documentation of prior HBV vaccination, and subjects who have negative HBsAg, positive HBcAb and positive HBsAb are required to undergo HBV DNA testing at the screening visit. Refer to [Appendix 5](#) for the detail of HBV screening.

### **7.2.6.3. Tuberculosis Screening**

During the screening period, it must be determined and documented that a subject does not have evidence of active or latent or inadequately treated infection with TB per the inclusion criteria. The results of TB screening conducted in 12 weeks prior to Screening or during the screening period must be documented in study records prior to Baseline/Day 1.

#### **7.2.6.3.1. Whole blood IFN- $\gamma$ release assay**

QFT-G is an *in vitro* diagnostic test using a peptide cocktail simulating ESAT-6, CFP-10 and TB 7.7 proteins to stimulate cells in heparinized whole blood. Detection of IFN- $\gamma$  performed by Enzyme-Linked Immunosorbent Assay (ELISA) is used to identify *in vitro* responses to these peptide antigens that are associated with *Mycobacterium tuberculosis* infection. QFT-G is an indirect test for *M. tuberculosis* infection (including disease) and is intended for use in conjunction with risk assessment, radiography and other medical and diagnostic evaluations.

The T-SPOT® TB test is an IFN- $\gamma$  release assay, and enumerates the response of effector T cells that have been sensitized to *Mycobacterium tuberculosis*. IFN- $\gamma$  is captured and presented as spots from T cells sensitized to *Mycobacterium tuberculosis* antigens. The results are interpreted by subtracting the spot count in the negative (NIL) control from the spot count in Panels A (ESAT-6) and B (CFP-10).

A negative QFT-G and/or T-SPOT test result is required to meet the inclusion criterion. QFT-G and T-SPOT test results will be reported as positive, negative or indeterminate. In the case of an indeterminate result, repeat tests should be permitted for the purpose of determining eligibility of subjects to enroll in this study. Mantoux/PPD testing will be allowed, if there are two consecutive indeterminate results in subjects who have been received BCG vaccination. Subjects with a history of BCG vaccination will be tested with the QFT-G and/or T-SPOT test.

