	Screening	Baseline Day 1	Week 4	Week 8	Week 12 (EOS/ET) 
Study Day	-27	1	29	57	85
Visit Window (Days)	+7 (i.e. -34 to 0)	0	±3	±3	±3
FACIT- Fatigue Scale		X			X
Euro Quality of Life Questionnaire (EQ-5D)		X			X
Randomization		X			
Study Drug Dispensing-New bottles supplied		X	X	X	
Dispense Dosing Diary		X	X	X	
Drug Accountability			X	X	X
Review of subject Dosing Diary			X	X	X
Adverse Events		X	→	→	X

- Study procedures to be performed at the End of Study (EOS) or Early Termination (ET) Visit.
- Medical history includes previous vaccination history, smoking status, average weekly alcohol consumption, family history of premature coronary heart disease (CHD), history of any prior episodes of herpes zoster and confirmation of RA diagnosis.
- Complete physical exam includes height, weight, general appearance, skin (presence of rash), HEENT (head, eyes, ears, nose and throat), lungs (auscultation), heart (auscultation for presence of murmurs, gallops, rubs), lower extremities (peripheral edema), abdominal (palpation and auscultation), neurologic (mental status, station, gait, reflexes, motor and sensory function, coordination) and lymph nodes.  
Targeted physical exam includes weight, examination of heart, lungs, lower extremities for peripheral edema, abdomen and lymph nodes.
- Temperature will be collected as axillary temperature. The same method should be used throughout the study.
- Mantoux Purified Protein Derivative (PPD) tuberculin skin test will be allowed, if there are two consecutive indeterminate results of QFT-G or T-SPOT test in subjects who have not received Bacille Calmette Guérin (BCG) vaccination during screening period.
- Chest X-ray (PA and lateral) or chest CT scan (with or without IV contrast) must be obtained at screening or within 12 weeks prior to screening and read by a qualified radiologist or respiratory therapist. If necessary, a chest CT scan (with or without IV contrast) may be performed during screening following initial performance of chest radiographs (PA and lateral) at the clinical discretion of the investigator. If pulmonary signs and symptoms are observed at and after baseline visit, unscheduled imaging test (e.g. chest X-ray or chest CT scan) may be performed based on the judgment by investigator as appropriate.
- Hematology includes hemoglobin, hematocrit, red blood cell (RBC) count, white blood cell (WBC) count with differential and platelet count.

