10. Subjects receiving non-prohibited concomitant medications for any reason must be on a stable regimen, which is defined as not starting a new drug or changing dosage within 7 days or 5 half-lives (whichever is longer) prior to baseline visit, or as defined in Concomitant Medications (refer to section [5.8.1](#) and [5.8.2](#)).
11. Female subjects of childbearing potential must have negative pregnancy test results at screening and baseline visit.
12. Female subjects who are not of childbearing potential (ie, meet at least 1 of the following criteria):
  - Have undergone a documented hysterectomy and/or bilateral oophorectomy;
  - Have medically confirmed ovarian failure; or
  - Achieved postmenopausal status, defined as follows: cessation of regular menses for at least 12 consecutive months with no alternative pathological or

physiological cause; a serum follicle stimulating hormone (FSH) level within the laboratory's reference range for postmenopausal women.

13. No evidence of active or latent or inadequately treated infection with *mycobacterium tuberculosis* (TB) as defined by meeting both criteria "a" and "b" below:

- a. Chest radiographs (PA and lateral) or chest CT scan (with or without IV contrast), taken at or within 12 weeks prior to screening visit, without changes suggestive of active TB infection as determined by a qualified radiologist or a respirologist. If necessary, a chest CT scan (with or without IV contrast) may be performed during screening following initial performance of chest radiographs (PA and lateral) at the clinical discretion of the investigator.
- b. Subjects who correspond to any of the following
  - 1) A negative test for blood IFN- $\gamma$  release assay, i.e. Quantiferon-3G/QuantIFERON® TB Gold In-tube (QFT-G) or T-SPOT test, performed at or within 12 weeks prior to screening visit.

Note 1)

Subjects with a history of *Bacille Calmette Guérin* (BCG) vaccination **MUST** be tested with the blood IFN- $\gamma$  release assay.

Note 2)

In subjects who didn't receive BCG vaccination, if there are two consecutive indeterminate results of QFT-G or T-SPOT test, a Mantoux/ Purified Protein Derivative (PPD) tuberculin skin test will be allowed during screening period. A negative Mantoux/PPD tuberculin skin test result is required to meet the inclusion criterion.

Note 3)

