#### **7.2.6.3.2. Mantoux/Purified Protein Derivative (PPD) Tuberculin Skin Test**

Mantoux Purified Protein Derivative (PPD) tuberculin skin test will be allowed during screening period, if there are two consecutive indeterminate results of QFT-G or T-SPOT test in subjects who have not received BCG vaccination. Subjects must have a Mantoux/PPD tuberculin skin test administered and then evaluated by a health care professional 48 to 72 hours later. If performed, a negative Mantoux/PPD tuberculin skin test result is required to meet the inclusion criterion.

The Tuberculin Test consists of intracutaneous injection of PPD in 0.1 mL of solution on the volar aspect of the forearm, using a short beveled 26-or 27-gauge needle (Mantoux test). The test is positive if the diameter of the erythema is over 10 mm in 48 to 72 hours after injection.

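### Protocol Section 7.2.6.3.1 reverses the BCG condition for the tuberculin skin-test fallback, and Table 5 sends sites to that section without stating any BCG condition

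*Protocol*

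**What the plan says.** Criterion 13 b 1) in Protocol Section 4.1 asks for a negative blood assay (QFT-G or T-SPOT). Note 1 makes that assay mandatory for anyone with a history of BCG vaccination. Note 2 provides a skin-test fallback and names its group: "In subjects who didn't receive BCG vaccination, if there are two consecutive indeterminate results of QFT-G or T-SPOT test". It then gives the result a role in eligibility: "A negative Mantoux/PPD tuberculin skin test result is required to meet the inclusion criterion".

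Two other places agree on the group. Footnote 5 of the Schedule of Activities allows the skin test "if there are two consecutive indeterminate results of QFT-G or T-SPOT test in subjects who have not received" BCG. Section 7.2.6.3.2, which is devoted to the skin test, allows it "if there are two consecutive indeterminate results of QFT-G or T-SPOT test in subjects who have not received BCG vaccination" and adds: "If performed, a negative Mantoux/PPD tuberculin skin test result is required to meet the inclusion criterion".

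Section 7.2.6.3.1, on the blood assay, says the reverse: "Mantoux/PPD testing will be allowed, if there are two consecutive indeterminate results in subjects who have been received BCG vaccination".

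The comment in the assay row of Table 5 repeats the trigger of two consecutive indeterminate results and says the skin test can be done during screening. It does not mention BCG status and refers the reader to Section 7.2.6.3.1 alone.

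**The concern.** Read literally, Section 7.2.6.3.1 offers the skin test to the group that criterion 13 leaves out and says nothing of the group for whom the fallback was written. It swaps one group for the other; it does not add a second one. The text is the current Amendment 3 wording, not a remnant in the amendment history.

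The rule is one that sites act on. Staff who work from the laboratory table are sent to the one wrong statement and are not pointed to the section that has it right. Two errors could follow.

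- A BCG-vaccinated subject with two indeterminate assays is skin-tested and entered on a negative result. Criterion 13 does not admit a subject by that route, and SAP Section 5.6.1 counts any such entry as a protocol deviation.
- An unvaccinated subject with two indeterminate assays is screened out because Section 7.2.6.3.1 shows no fallback, although Note 2 provides one.

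The protocol's background section lists tuberculosis among the important safety risks of tofacitinib, so the screening rule should read the same wherever it appears.

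**Working it through.** No arithmetic on sample size, error rate or margin is involved. The check is a comparison of every place that states the fallback. Section 6.1 lists the assay among the screening procedures but states no skin-test fallback, so there are five.

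| Place in the protocol | BCG status required for the skin test | Says a negative skin test is needed for inclusion? |
|---|---|---|
| Section 4.1, criterion 13 b 1) Note 2 | Not vaccinated | Yes |
| Schedule of Activities, footnote 5 | Not vaccinated | No, only allows the test |
| Section 7.2.6.3.2 | Not vaccinated | Yes |
| Section 7.2.6.3.1 | Vaccinated | No, only allows the test |
| Table 5, assay row | None stated; refers to Section 7.2.6.3.1 | No, only allows the test |

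By BCG status: 3 not vaccinated + 1 vaccinated + 1 silent = 5. By role of the result: 2 tie it to inclusion + 3 only allow the test = 5. Both of the places that tie it to inclusion limit the fallback to subjects without BCG.

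**Which version is intended?** Three points lead to the same answer.

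1. Section 7.2.6.3, which introduces TB screening, defers to the inclusion criteria, so criterion 13 is the reference text.
2. Note 1 of criterion 13 requires the blood assay for BCG-vaccinated subjects, which fits a skin-test fallback reserved for the others.
3. Section 7.2.6.3.1 itself continues: "Subjects with a history of BCG vaccination will be tested with the QFT-G and/or T-SPOT test". That sits badly with a skin-test fallback for the same subjects one sentence earlier. The faulty grammar of the reversed sentence also suggests a slip for the negative form.

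**How far could the error carry?** Section 7.2.6.3.1 also states: "A negative QFT-G and/or T-SPOT test result is required to meet the inclusion criterion". A site that applies this sentence would not enter a subject on a skin test alone. The section never says that a negative skin test makes a subject eligible.

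**Does it reach the analysis?** The full analysis set in SAP Section 5.1 keeps every subject who was randomized and dosed. The per-protocol set in SAP Section 5.2 excludes only for deviations that could affect efficacy, and the documents do not say that a TB-screening error is one of these. No effect on the primary comparison follows.

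**The case against.** The strongest reply is that this is one missing word that any attentive reader can resolve. The eligibility criterion is correct, the Schedule footnote is correct, and the section dedicated to the skin test comes straight after the faulty one and is also correct. Eligibility is reviewed and documented before inclusion, reviewed again at baseline, and attested by the investigator before randomization. For a wrong entry, a site would have to overlook all of this and two further sentences in Section 7.2.6.3.1. An unvaccinated subject would lose the fallback only if the site read that section in isolation, since it does not forbid the test in that group. The Table 5 row concerns the assay, so a reference to the assay section is natural, and once that section is corrected the reference leads to the right rule.

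Much of this stands. Wrong entry is unlikely at a careful site, the intended rule is not in doubt, and the Table 5 changes matter less than the correction to Section 7.2.6.3.1. Table 5 does state a condition, namely two indeterminate results; only the BCG condition is absent. None of this removes the contradiction. The reversed sentence is in an operative screening procedure, it names the wrong group, and the laboratory table leads to it.

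**Conclusion.** The concern holds. Section 7.2.6.3.1 contradicts criterion 13, Schedule footnote 5 and Section 7.2.6.3.2 on who may have the skin test, and Table 5 leaves out the BCG condition while pointing only to the contradictory section: three places against one, with one silent. The direction of the correction is settled by the protocol itself.

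The consequence is confined to consistent TB screening and to occasional eligibility errors, in either direction. The documents give no frequency of BCG vaccination or of repeated indeterminate assays, and none is assumed, so the number of subjects affected cannot be estimated. No increase in TB risk and no effect on the non-inferiority analysis is claimed. The conclusion rests only on the wording of the protocol and on the deference in Section 7.2.6.3 to the inclusion criteria. The text should be corrected because the error is plain and the correction involves no trade-off.

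**What to change.** In Section 7.2.6.3.1, change the BCG clause so that the skin test after two consecutive indeterminate assays is limited to subjects who have not had BCG, matching criterion 13 b 1) Note 2 and Section 7.2.6.3.2. This is the essential change.

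In Table 5, add the same condition to the comment on the assay row and have it refer to Section 7.2.6.3.2 as well as Section 7.2.6.3.1, so that a site working from the table reaches the full rule.

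The cost is one sentence and one table comment in a protocol amendment. The eligibility criteria stay as they are, and no procedure is added.
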